Individuals between the ages of 40-65, regardless of why they visit any of the committed health choice units, will be asked to participate by asking if they are insufficiently physically active (<150 minutes per week at moderate intensity or <75 minutes per week at high intensity).

Exclusion Criteria: Dementia, severe mental disorder, new-onset untreated untreated unstable anginapectoris, or myocardial infarction within 6 weeks prior to study entry. Those with physical disabilities that prevent physical activity and individuals who do not master the Swedish language in speech and writing will be excluded. Patients who have abnormal values according to guidelines that require same-day or weekly medical consultation.

Procedure Inclusion

At the care units, everyone who visits will be asked about study participation. There will be posters with information at the entrances and in other suitable places. Those who wish to participate in the study agree to this by signing informed consent after receiving oral and written information. Information about the study will be provided by the district nurse/nurse involved in the study, who will then also collect the informed consent. The opportunity to ask questions about the study will be repeated at subsequent visits as well as an opportunity to discontinue their participation. The potential research subject should estimate their physical activity level in minutes per week for inclusion assessment. The research subjects are asked to come one morning for fasting blood sampling.

Measurement methods

Physical activity; Health-promoting physical activity is any physical activity that improves health and physical capacity without causing harm or posing a risk. The international recommendation of the WHO (2011) (38) is at least 150 minutes of physical activity per week at moderate intensity, or at least 75 minutes at high intensity. Intensity refers to how strenuous the activity is. Moderate intensity refers to housework, gardening, brisk walks or the like. High intensity refers to running, swimming, aerobics, or similar.

Accelerometer: The Actigraph GT3X is a digital motion meter that will be attached to the subject at waist height. The accelerometer records the time in motion as well as the time inactivity. Over a seven-day period, about 40,000 measurement points are collected per accelerometer.

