FFMQ (Five Facets of Mindfulness); is an instrument that measures five aspects of mindfulness. It consists of 29 statements where it is assessed on a five-point scale how well the statement is true "Never/almost never", "Rarely", "Sometimes", "Often" or "Always". In the compilation, the answers are graded from one to five, grouped and analyzed based on the five aspects of mindfulness (84, 85). The aspects that are measured are the ability to: Observe, Not react (in the face of inner experiences), Describe, Not judge and Act consciously. ISI (Insomnia Severity Index); is a self-assessment questionnaire that measures insomnia in order to quickly obtain a measure of the severity of sleep disorders. The scale consists of 7 questions that evaluate falling asleep, sleep during the night, early waking up, the feeling of being rested, how the sleep problems affect daily life and how the sleep pattern worries the individual. For each question, the participants must take a position on how they have experienced their sleep habits over the past two

7

weeks and grading the answers from 0 to 4, where 0 stands for "not at all" and 4 stands for "very". Scores between 0 to 7 indicate the absence of significant sleep problems. Scores from 8 to 14 show some sleep problems but not as a sleep disorder. Scores from 15 to 21 indicatearcclinically significant moderate sleep disorder. Scores between 22 and 28 indicate clinically significant severe sleep problems (86, 87). Self-rated health; Self-rated health encompasses all the different dimensions of the individual, physical, mental as well as social (46). The individuals' self-perceived health is estimated through a simple question- How do you think your general health is in relation to peers- with fiveanswer alternatives; Very good, good, somewhat, bad or very bad (47-49).

Initial visit

At the visit, participants will provide blood samples, measurement of body constitution and vital parameters, and submit completed questionnaires for mapping the hereditary prevalence of cardiovascular disease and lifestyles, and will receive accelerometers to be worn for one week until the follow-up visit. The results from the sampling here constitute the study's baseline.

The visit includes:

1. Information about the study

2. Written informed consent

Questionnaires:1) Country of birth,2) Occupation4) Illness5) Medication

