6) Family history/hereditary (siblings and parents). coronary artery disease, stroke, venous thrombosis, diabetes, hypertension7) Self-assessment of lifestyle habits according to the National Board of Health and Welfare's elaborated questions regarding lifestyle habits.8) Mindfulness assessment with FFMQ9) Self-assessment sleep with ISI

Clinical examination:

1) Length

2) Weight3) Blood pressure.

Sampling:

Plasma samples and whole blood are taken fasting for;

1) Cholesterol, triglycerides, HDL, LDL.2) fP-glucose3) Venous blood samples for later analysis of biomarkers such as proteins, DNA, RNA and

miRNAs in order to see if they can be used as prognostic biomarkers, but also to see any change after intervention. We will also analyze telomer lengths in blood using qPCR method to see the association between risk of disease but also change after intervention. Please note that those who have given consent have also given consent for us to analyze their samples even if they choose to drop out before the intervention.

Follow-up visits

The individuals who wish to participate and meet the inclusion criteria will be offered a health consultation with the district nurse for review of collected material, blood samples and questionnaires. All patients who have abnormal values according to established guidelines will follow the flow chart for usual treatment. At this visit, inclusion and exclusion criteria are checked and the patient is again informed and has the opportunity to ask questions about the study. Patients who join the study will be randomized to either mindfulness, mindfulness with FAR®, or FAR® alone. Everything is documented partly in patient records but also in patient forms (case report form; CRF) together with the serial number.

The visit includes:

- 3. Feedback on collected information
- 4. Position on inclusion/exclusion criteria
- 5. Any additional measurements and sampling

Randomization

The randomization takes place after the inclusion in the study but before the follow-up visit where the research subject will find out which group they belong to. After inclusion, a commercial email is sent with serial number, gender and age to the contact person ([contact])

which makes a computerized randomization based on chance. The patient or staff cannot choose which group they should belong to.

Serial number

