The primary intervention outcome was a change in the level of physical activity, self-reported and measured by ACTi Graph GT1X activity monitors. We used the same definitions and methods to handle the activity monitor data as in previously published research regarding physical activity [1, 2]. Activity monitor data were divided into sedentary, light physical activity (LIPA) and moderate to vigorous physical activity (MVPA). The participants were instructed to wear the activity monitor daily for a week before randomisation, at 3 months and at 6 months follow-up. Wear time was defined by subtracting non-wear time from 24 hours. Non-wear time was defined as at least 60 consecutive minutes with no movement (0 counts per minute), with allowance for a maximum of 2 min of counts between 0 and 100 [1, 3]. We considered ≥ 600 min wear time per day for at least 4 days to be valid compliance [1, 2]. Due to a small sample size, we did not demand four consecutive days with valid wear time, and we did not differ between weekdays and weekends. The average was expressed as total counts divided by wear time in minutes per day (counts per minute) and averaged over worn days. Registrations below 100 counts per minute were determined as being sedentary [1, 2, 4]. 100-2019 counts per minute were considered LIPA, and > 2020 counts per minute as MVPA [1, 2]. The results are presented as percentage sedentary, LIPA or MVPA per valid day and averaged over the number of valid days [2] self-reported daily activity (e.g. gardening, slow walks, biking) was measured by an eight-step scale ($0 = 0 \text{ min/week}, 7 \ge 300 \text{ min/week}$), and selfreported leisure time activity (e.g. running, football) was measured by a seven-step scale (0 =0 min/week, $6 \ge 200$ min/week).

Secondary intervention outcomes

Change in self-rated health (SRH) between baseline and follow-up, measured with a five-step scale (1–5): very poor, poor, fair, good or very good.

Change in blood pressure, weight or serum lipids between baseline and follow-up.

Change in insomnia problems as measured with insomnia severity index (ISI) [5] between baseline and follow-up.

Change in mindfulness was measured with five facets of the mindfulness questionnaire (FFMQ) [6] between baseline and follow-up.

Statistical methods

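### The protocol gives two orders for randomisation and the final eligibility check, and one of them lets exclusions and withdrawals depend on the arm

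*Protocol*

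**What the plan says.** The protocol describes an initial visit (consent, blood samples, questionnaires, accelerometer handed out), about a week of accelerometer wear, and then a follow-up visit with the district nurse.

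- Protocol, Randomization: "The randomization takes place after the inclusion in the study but before the follow-up visit", and that visit is "where the research subject will find out which group they belong to". The allocation is requested by e-mail from a contact person, who makes it by computer.
- Protocol, Follow-up visits: "At this visit, inclusion and exclusion criteria are checked and the patient is again informed". The list of what the visit contains includes "Position on inclusion/exclusion criteria". The same section states: "Patients who join the study will be randomized to either mindfulness, mindfulness with FAR®, or FAR® alone".
- Protocol, Inclusion/exclusion: one excluded group is "Patients who have abnormal values according to guidelines that require same-day or weekly medical consultation". The blood results needed to apply this are reviewed at the follow-up visit.
- Protocol, Procedure Inclusion: consent is signed at the start, and patients may stop at later visits.
- Protocol, Interruption: someone whose participation is broken off no longer counts as a member in the analysis, and no substitute is recruited.
- SAP, Randomisation and Statistical methods: allocation is by minimisation on age and sex with a random element. No intention-to-treat set is named, and exclusions after randomisation are not addressed.

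**The concern.** Randomisation protects the comparison only if the set of people being compared is fixed before the arm can influence it. If eligibility and joining are settled at a visit that comes after allocation, and the arm is disclosed at that visit, the people who remain can differ between arms for reasons linked to the arm.

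The arms make this plausible. Two of them ask for eight weekly group sessions and 20 minutes of daily practice; the third asks for neither. A patient who does not want that commitment has a reason to leave, or to be judged unsuitable, in the mindfulness arms only. Some exclusions, such as severe mental disorder or a disability that prevents activity, need judgement. The people lost would tend to be the less motivated, and motivation bears directly on adherence to prescribed activity. Taking them out of the analysis would make the remaining mindfulness participants look better than their arm as randomised, and could weaken the age and sex balance that minimisation provided.

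**Working it through.** The plan has no figure of its own on this point, so the main check is to set the sections side by side.

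**Step 1. Two orders of events.**

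| Protocol section | Order implied |
|---|---|
| Randomization | inclusion → randomisation → follow-up visit (arm disclosed) |
| Follow-up visits | visit: results reviewed, criteria checked, patient informed again → those who join are randomised |

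Both cannot be followed. In the first order the criteria check comes after allocation; in the second it comes before.

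**Step 2. Is the check at the visit a formality?** Not entirely. The abnormal-values exclusion depends on baseline results, and the visit is where those are reviewed. At least one criterion may therefore still be open when the Randomization section has the arm already assigned.

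**Step 3. What happens to people lost at that point?** The Interruption section takes interrupted participants out of the analysis. The SAP names no analysis set that would put them back. Its linear mixed model can use whatever measurements a person has, but someone who leaves at the follow-up visit has only baseline data.

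**Step 4. Possible size on a continuous outcome.** Let a fraction f of one arm be removed, with mean outcome d SD below the rest. If the rest have mean m, the full arm has mean (1 − f)m + f(m − d) = m − fd. After removal it is m, so the arm's mean shifts by f × d. Both inputs are assumptions.

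- f = 0.10 (about 3 of 29 people; 88 included / 3 arms ≈ 29), d = 0.5 to 1: 0.05 to 0.10 SD.
- f = 0.20, d = 0.5 to 1: 0.10 to 0.20 SD.

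For scale, the standard error of a difference between two arms of 29 is √(2/29) = 0.26 SD. The 10% case is 0.05/0.26 to 0.10/0.26, about 0.2 to 0.4 standard errors; the 20% case reaches 0.20/0.26, about 0.8.

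With the protocol's full-scale 321 per group, before dropout, the standard error is √(2/321) = 0.079 SD. The same 0.05 to 0.20 SD is then about 0.6 to 2.5 standard errors. This bias does not shrink as the trial grows.

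**Step 5. Possible size on the adherence scale.** Assume true adherence of 50% in both arms, and that everyone removed from one arm is a non-adherer, which is the extreme case. Observed adherence in that arm is 0.5/(1 − f).

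| f | Observed | False gain |
|---|---|---|
| 0.05 | 52.6% | 2.6 points |
| 0.10 | 55.6% | 5.6 points |
| 0.20 | 62.5% | 12.5 points |

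The planned effect is 62.5 − 50 = 12.5 points, so the last row equals it. That row is an upper bound for 20% removal, not a forecast.

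**The case against.** A reader might infer that allocation concealment is broken. The documents do not support that. Consent is signed before randomisation, the allocation is made remotely by computer with a random element, and the protocol states that neither patient nor staff can choose the group. Nobody enrolling a patient can foresee or pick the arm. The weakness lies in who stays after allocation.

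A reader might also infer that sites hold the allocation while they apply the exclusions. The documents say only that the patient learns the arm at the visit. They do not say when staff learn it, or at what point in the visit it is disclosed.

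The protocol also contains text that points towards early inclusion. Patients estimate their activity for the inclusion assessment before baseline sampling, the follow-up visit is offered to those who wish to take part and meet the inclusion criteria, and people unwilling to be included are not randomised. The check at the visit can be read as a re-check, and those who leave there as consented participants withdrawing. This narrows the problem. It does not remove it, because the abnormal-values exclusion still depends on results reviewed at that visit, and the text still treats joining as undecided there.

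The accelerometer timing is not a contradiction. Wear "will receive accelerometers to be worn for one week until the follow-up visit" and the SAP's instruction to "wear the activity monitor daily for a week before randomisation" both fit randomisation at the end of the wear week, so they do not settle the order.

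Finally, reordering cannot stop someone from joining, learning the arm and then withdrawing, as in any open-label trial. That stands, and it is why the analysis rule has to change as well. I have not seen the study flowchart, which is a figure; it may show the intended order, but the two sections would still disagree.

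**Conclusion.** The concern holds as an internal contradiction with a real consequence. Followed as the Randomization section is written, the plan does not protect against exclusions and withdrawals that depend on the arm, and the Interruption section would then drop interrupted people from the analysis.

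The size of any bias is unknown, because the documents report no number of people lost at this visit. Under the assumed removal of 10% to 20% of one arm at 0.5 to 1 SD worse, it is about 0.05 to 0.20 SD. That is below one standard error in a pilot of this size, but not negligible against the precision of the full-scale study. If sites in fact followed the Follow-up visits section, selective exclusion before allocation does no harm to the comparison, and only later withdrawals remain to be handled.

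**What to change.** 1. Reconcile the two sections. In Randomization, delete the clause that places randomisation before the follow-up visit. State that three things are recorded in the CRF before the allocation e-mail is sent: that all inclusion and exclusion criteria are met (blood results included), that the baseline accelerometer week is complete, and that the patient confirms joining. The arm is disclosed only afterwards, at the end of the visit or by telephone or letter. Anyone found ineligible is then a screening failure and not a randomised participant.
2. Amend Interruption, and add to the SAP, that everyone randomised is analysed in the allocated arm using all available data.
3. For the 88 participants already included, report by arm how many were excluded or withdrew after randomisation, with timing and reason.

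The cost is protocol wording, a site instruction and a short wait before the patient learns the arm. Item 1 can help only future participants, that is, the full-scale study still to be planned. Items 2 and 3 apply to the pilot as well, although item 2 cannot recover outcomes that were never measured in people who left at the follow-up visit.

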[figure not shown]
Samples for freezing

Participating health choice units perform venous sampling of the research samples according to the sampling kits sent out. This also means assisting in sending the marked test tubes to the laboratory for further handling and transport to the CPF. This refers to sampling before and after intervention and during follow-up. This means sampling at 0 months, 3 months, 6 months and at full study also at 12 months, which means four occasions per participant.

Tests and procedures

In vitro kits, including referrals, instructions and labels for labelling, will be prepared at the CPF laboratory and packed in boxes, one per participant and sampling. These boxes will be distributed to the participating health choice units. The unused tubes should be returned to the CPF after the study is completed. A detailed annex to instructions will be prepared by the CPF. The samples to be submitted to the CPF are marked with the date and the participant's serial number. Blood volume is 36 ml per test batch, a total of 108 ml after three rounds of tests and 144 ml after four rounds. It must be noted in the patient's medical record that samples have been taken as part of a research study.

Study Flowchart

Outcome measures

Association between self-rated health, lifestyle habits, heredity for cardiovascular disease, physical activity level, vital parameters and blood tests.

Change in physical inactivity and activity

Difference in inactivity between intervention group and control group as measured by accelerometer

Change in self-rated worry and anxiety according to PHQ 9 after intervention

Change in Conscious Presence According to FFMQ After Intervention

Change in sleep according to ISI after intervention

Differences in biomarker levels between the different intervention groups

Power calculation

We will carry out a pilot study in order to make a more accurate power calculation which will be based on the results of the pilot study (89). We plan to include 30 people per group in the pilot study, a total of 90 people.

The sample size for a full-scale intervention study with follow-up is based on a 1:1 ratio between the groups and calculated to N=321 in the intervention group and N=321 in the control group per group based on a power analysis with 5% significance level and 80% power. The non-response rate is calculated at about 30%. The calculation is based on other studies with compliance to physical activity on prescription as an outcome measure, where 50% of the individuals followed the recommendation on physical activity based on FAR,@ we expect an increase of 25% from 50% to 62.5% adherence

Data analysis

Group comparison analysis will be conducted using chi-2 test for categorical variables. Quantitative variables will be analyzed with ANOVA or Kruskal-Wallis prenormal-distributed and non-normally distributed variables, respectively. Correlations between different variables will be investigated using regression analyses (90).

Safety and ethical aspects

Participants in all groups are contacted by a doctor according to a flow chart if abnormal measurements appear or if physical symptoms occur during intervention that need to be assessed by a doctor. Conversations about lifestyle habits can raise thoughts and concerns about personal health, and if necessary, there will therefore be the opportunity to get feedback via the district nurse or your regular doctor. Personal identity number and name will be replaced with a serial number that follows the form and

samples through the study, which means that all data during analysis is completely without personal data and only marked with serial number. The identification lists will be kept at the health choice units until the analyses are completed, after which the identification lists will be stored at the CPF in a secure manner so that no unauthorised person can access them. Presentation of results from the study will take place at group level, which means that it is not possible to identify individuals. The individuals included in the study are covered by the Patient Injury Act (1996:799) as they are patients at visits to the health choice unit and are covered in clinical research by the same protection as if they were only patients. The study has received ethical approval from the Regional Ethics Review Board in Lund (2016/404). The study is registered on clinicaltrials.gov(20160826) rainr NCT02869854.

Economics

The research subjects participating in the study do not receive any compensation for loss of income or travel. Visits to the district nurse are currently free of charge, in the event of the introduction of a possible fee for visits to the district nurse, this should not affect the patients included in the study. The visits that may be relevant with a cost are if there is a need for treatment of a doctor/counsellor/physiotherapist contact. The health choice units are compensated with SEK 1200 per patient for the intrusion into the activities, which includes sampling and collection of data for the study. This refers to sampling before and after intervention and at follow-up after 3, 6 and 12 months. In total, the pilot study involves about 90 patients, 30 people in each group.

CPF covers the cost of all test tubes and blood analyses included in the study. CPF is responsible for pre-printing forms, envelopes and return postage.

Expected benefits

Prevention of cardiovascular disease is of paramount importance as this is the most common cause of death in Sweden. Primary and secondary prevention of cardiovascular diseases means reduced suffering for patients and great socio-economic benefits (3). By reducing inactivity, the risk of developing the disease can be reduced. Measurement of self-rated health creates the conditions for patient-centred care by starting from the patient's experience. Patients perceive it as important to work with lifestyle habits in primary care (91) as health risks can be detected. Through lifestyle counselling in primary care, patients can receive guidance to a healthier life (91-93). For the health choice units, this can lead to a more structured work on lifestyle habits and increased coverage, which can have a positive impact on the health choice units' finances. For the staff concerned, this can lead to increased job satisfaction.

Timetable

The pilot study is scheduled to begin in September 2016 and is expected to last no later than December 2019, The number of individuals included in the pilot study amounts to 88 individuals (180829). Full-scale study will be planned according to Power calculation based on pilot study. Analysis of collected blood samples in the biobank will be analyzed during the spring from February 2019 to December 2019 including statistical analysis and report writing.

References

